9. Has an active auto-immune disease requiring systemic treatment within the past 3 months or a documented history of clinical autoimmune disease in the past, or a syndrome that requires systemic steroids or immunosuppressive agents. Subjects with vitiligo or resolved childhood asthma/atopia would be an exception to this rule. Subjects that require intermittent use of bronchodilators or local steroid injections would not be excluded from the study. Subjects with hypothyroidism stable on hormone replacement or Sjorgen's syndrome will not be excluded from the study.
10. Has evidence of interstitial lung disease or active, non-infectious pneumonitis.
11. Has an active infection requiring systemic therapy.
12. Has a history or current evidence of any condition, therapy, or laboratory abnormality that might confound the results of the trial, interfere with the subject's participation for the full duration of the trial, or is not in the best interest of the subject to participate, in the opinion of the treating investigator.
13. Has known psychiatric or substance abuse disorders that would interfere with cooperation with the requirements of the trial.

14. Is pregnant or breastfeeding, or expecting to conceive or father children within the projected duration of the trial, starting with the pre-screening or screening visit through 120 days after the last dose of trial treatment. Pregnant women are excluded from this study because vorinostat, tamoxifen and PD-1 are drug classes with the potential for teratogenic or abortifacient effects. Because there is an unknown but potential risk for adverse events in nursing infants secondary to treatment of the mother, breastfeeding should be discontinued if the mother is treated with vorinostat, tamoxifen and PD-1 inhibitors.
15. Active and ongoing steroid use, except for non-systemically absorbed treatments (such as inhaled or topical steroid therapy for asthma, COPD, allergic rhinitis).
16. Major surgery \leq 2 weeks prior to starting a study drug or who have not recovered from side effects of such therapy.
17. Known hypersensitivity to pembrolizumab or any of its ingredients.
18. Has received a live vaccine within 30 days prior to the first dose of trial treatment.

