> 5 x ULN	First occurrence: hold until \leq grade 2, resume at 75 %: 300 mg qd Second occurrence: Hold until grade 2 or less, 50 %: 200 mg qd Third occurrence: remove from study	100%

Hepatic Dysfunction: Any new increase in LFTs should raise the concern to rule out progressive metastatic disease. If the rise is not due to progressive metastatic disease, give the following dose based on lab values obtained on day 1 of each cycle:

Effects on the liver: Tamoxifen has been associated with changes in liver enzyme levels, and on rare occasions, a spectrum of more severe liver abnormalities including fatty liver, cholestasis, hepatitis and hepatic necrosis. A few of these serious cases included fatalities. In most reported cases, the relationship to tamoxifen was uncertain. However, some positive rechallenges and dechallenges have been reported. If grade 3 or 4 liver toxicity is maintained after a temporary stopping of vorinostat, both drugs should be stopped. Any rechallenge should be discussed with the study chair. **If treatment is delayed for more than 3 weeks, contact the Principle Investigator.**

Gastrointestinal Toxicity

Nausea/Vomiting/Dehydration: In this protocol, the routine use of any and all anti-emetics is allowed as clinically appropriate; these include the use of dexamethasone and 5-HT3 receptor antagonists.

Patients should maintain adequate fluid and food intake because vorinostat's dose-limiting toxicities are anorexia, dehydration, diarrhea, and fatigue. In the setting of dysgeusia, popsicles and Gatorade have been found to be useful by some investigators to maintain adequate hydration. Patients should also be encouraged to seek a nutritional consult.

Diarrhea: Treat diarrhea promptly with appropriate supportive care, including loperamide. Instruct patients to begin taking loperamide at the first signs of: 1) poorly formed or loose stool, 2) occurrence of more bowel movements than usual in one day, or 3) unusually high volume of stool. Loperamide should be taken in the following manner: 4 mg at first onset of diarrhea then 2 mg after each unformed stool. The daily dose should not exceed 16 mg. Loperamide should not be taken prophylactically. Advise patients to drink plenty of clear fluids to help prevent dehydration caused by diarrhea. Avoid loperamide if there is the presence of blood or mucus in the stool or if

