6.3 Usage of Concurrent/Concomitant Medications

6.3.2 Acceptable Concomitant Medications

All treatments that the investigator considers necessary for a subject's welfare may be administered at the discretion of the investigator in keeping with the community standards of medical care. All concomitant medication will be recorded on the case report form (CRF) including all prescription, over-the-counter (OTC), herbal supplements, and IV medications and fluids. If changes occur during the trial period, documentation of drug dosage, frequency, route, and date may also be included on the CRF.

All concomitant medications received within 28 days before the first dose of trial treatment and 30 days after the last dose of trial treatment should be recorded. Concomitant medications administered after 30 days after the last dose of trial treatment should be recorded for SAEs and ECIs as defined in Section 7.2.

Anti-diarrheal and anti-emetic treatment may be given as required, either therapeutically or prophylactically, after such events have occurred in conjunction with a prior dose given without anti-diarrheals or anti-emetics. If needed, efforts will be made to standardize such supportive regimens in agreement with participating Investigators.

Other examples of supportive care medications include prophylactic or therapeutic use of erythropoietin for anemia and bisphosphonates (e.g., pamidronate).

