6.3.3 Prohibited Concomitant Medications

Subjects are prohibited from receiving the following therapies during the Screening and Treatment Phase (including retreatment for post-complete response relapse) of this trial:

- Anti-cancer systemic chemotherapy or biological therapy
- Immunotherapy not specified in this protocol
- Chemotherapy not specified in this protocol
- Investigational agents other than Pembrolizumab
- Radiation therapy
 - Note: Radiation therapy to a symptomatic solitary lesion or to the brain may be allowed after consultation with the study PI and Merck.
- Live vaccines within 30 days prior to the first dose of trial treatment and while participating in the trial. Examples of live vaccines include, but are not limited to, the following: measles, mumps, rubella, chicken pox, yellow fever, rabies, BCG, and typhoid (oral) vaccine. Seasonal influenza vaccines for injection are generally killed virus vaccines and are allowed; however intranasal influenza vaccines (e.g. Flu-Mist®) are live attenuated vaccines, and are not allowed.
- Glucocorticoids for any purpose other than to modulate symptoms from an event of clinical interest of suspected immunologic etiology. The use of physiologic doses of corticosteroids may be approved after consultation with the study PI and Merck.

Subjects who, in the assessment by the investigator, require the use of any of the aforementioned treatments for clinical management should be removed from the trial. Subjects may receive other medications that the investigator deems to be medically necessary.

The Exclusion Criteria describes other medications which are prohibited in this trial.

There are no prohibited therapies during the Post-Treatment Follow-up Phase.

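### Section 5.1.1.1 allows routine dexamethasone as an antiemetic, but section 6.3.3 prohibits glucocorticoids on treatment and has no antiemetic exception

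*Combined protocol and SAP*

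**What the plan says.** Section 5.1.1.1, under gastrointestinal toxicity, deals with nausea, vomiting and dehydration. It states that "the routine use of any and all anti-emetics is allowed as clinically appropriate; these include the use of dexamethasone and 5-HT3 receptor antagonists".

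Section 6.3.3 lists the therapies prohibited during the Screening and Treatment Phase. One entry is "Glucocorticoids for any purpose other than to modulate symptoms from an event of clinical interest of suspected immunologic etiology". The entry continues: "The use of physiologic doses of corticosteroids may be approved after consultation with the study PI and Merck". The section then says that subjects who, in the investigator's assessment, "require the use of any of the aforementioned treatments for clinical management should be removed from the trial".

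Three other places touch on the subject:

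- Section 6.3.2 allows antiemetics "either therapeutically or prophylactically, after such events have occurred in conjunction with a prior dose", and does not mention steroids.
- The nausea and vomiting guidance in sections 5.1.1.2 and 6.3.4 places prophylaxis in later cycles, according to institutional practice. It does not mention steroids either.
- Section 3.3.2 excludes at entry "Active and ongoing steroid use, except for non-systemically absorbed treatments".

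**The concern.** Two operative rules in the current text give opposite answers about the same drug. An investigator managing vorinostat-related nausea would look in section 5.1.1.1, find dexamethasone named as acceptable, and see no reference to section 6.3.3. An investigator who looked in section 6.3.3 would find the same prescription prohibited.

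What is at stake is how patients are managed. One site may give dexamethasone and keep the patient on treatment. Another may avoid it, or may take a patient judged to need it off the trial. Every arm includes a checkpoint inhibitor, and section 6.3.3 shows that the sponsor meant to restrict glucocorticoids. As written, section 5.1.1.1 works against that restriction.

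**Working it through.** No formula applies. The check is whether the two rules cover the same drug, the same patients and the same time, and whether any text reconciles them.

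1. **Same drug.** Section 5.1.1.1 names dexamethasone, which is a glucocorticoid. The entry in section 6.3.3 covers glucocorticoids for any purpose outside its exceptions.

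2. **Same patients and period.** The antiemetic sentence sits with the vorinostat and tamoxifen dose-modification tables, so one might think it governs a different setting. It does not. In the regimen tables of section 5.1, all three arms take vorinostat in all cycles and receive pembrolizumab from cycle 1 or cycle 2. The ban in section 6.3.3 is tied to the Screening and Treatment Phase, not to pembrolizumab dosing, so it also applies in cycle 1 of the arm that starts pembrolizumab in cycle 2.

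3. **The exceptions.** Section 6.3.3 has two.
   - Symptoms of an event of clinical interest of suspected immunologic origin. Ordinary drug-induced nausea is not such an event.
   - Physiologic doses, which may be approved after consultation with the study PI and Merck. Approval on consultation is not routine use, and section 5.1.1.1 sets no dose limit.
   
   Exceptions that cover routine antiemetic use: 0 of 2.

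4. **Possible reconciling text.** The closing permission in section 6.3.3 concerns medications other than those just listed, so it does not restore a listed one. Sections 5.1.1.2, 6.3.2 and 6.3.4 allow antiemetics in general terms and exempt no steroid from the ban. The steroid criterion in section 3.3.2 applies at entry and does not govern antiemetic use on treatment. No text settles which rule prevails.

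5. **A second mismatch in the same sentence.** Section 5.1.1.1 allows routine antiemetic use. Section 6.3.2 allows antiemetics, including prophylaxis, only after an event with an earlier dose. Deleting the word dexamethasone alone would leave this mismatch, and the remaining words would still admit any antiemetic, steroids included.

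6. **Size.** The rules apply to everyone enrolled. The planned range is 20 to 87 patients, and the ceiling of 3 arms × 29 = 87 is reached only if every arm completes its second stage. That is the scope of the rules, not a count of patients affected. The documents give no rate of antiemetic steroid use, so no such count can be derived.

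**The case against.** The strongest reply is that both sections can be obeyed at once: an investigator who uses only non-steroid antiemetics breaks neither. That is true, and it limits the practical weight of the point. It does not remove the defect, because an investigator who uses an express permission still commits a breach.

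A second reply is that the protocol itself calls for systemic corticosteroids elsewhere: for enterocolitis (sections 5.1.1.2 and 6.3.4), for pneumonitis of grade 2 or higher (section 5.1.1.3), and among the options for grade 3 or 4 infusion reactions. Some patients may therefore be exposed to steroids however the antiemetic sentence is settled. This stands. Any added effect of antiemetic dexamethasone is not established.

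A reader might infer more than the documents support, in three ways:

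- **That the secondary PD-L1 endpoint or the exploratory T-cell measures would be distorted.** Nothing in the documents says that antiemetic steroids alter these measures. An effect is possible but not shown.
- **That removals would bias the 24-week response rate.** Sections 3.5 and 6.2.2 keep patients who stop without progression in follow-up for disease status, although that follow-up ends if other cancer treatment starts. No effect on the primary endpoint is shown. The intention-to-treat statement in section 8.3.1 should not be offered as reassurance for every arm: it speaks of randomized patients, and section 3.6 says that ER-negative patients (Arm C) are not randomized.
- **That any patient given dexamethasone must leave the trial.** The removal sentence concerns subjects whom the investigator judges to require a prohibited treatment. A patient who merely received a dose has had a prohibited medication, but that sentence does not call for removal.

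**Conclusion.** The contradiction is real and should be corrected. Section 5.1.1.1 permits what section 6.3.3 prohibits, for the same patients over the same period in all three arms, and no other text reconciles the two. Using the permission breaches section 6.3.3 unless the purpose is an immune-related event of clinical interest or a physiologic dose has been approved.

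The conclusion rests on the wording alone, and on reading routine antiemetic use as outside both exceptions. The number of patients affected is unknown and no effect on any endpoint is shown. The case for acting is that the conflict bears on what investigators prescribe and on whether a patient stays in the trial, and that it can be removed cheaply.

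**What to change.** Replace the antiemetic sentence in section 5.1.1.1 with: *Non-steroid anti-emetics (e.g., 5-HT3 receptor antagonists) are allowed as clinically appropriate, subject to sections 6.3.2 and 6.3.3.* This removes the named steroid, the open-ended permission for any antiemetic, and the reference to routine use that does not fit section 6.3.2. No other section needs to change, including the recording rules in section 6.3.2.

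The cost is one amended sentence and the loss of one antiemetic option.

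If the sponsor does want antiemetic dexamethasone, the permission belongs in section 6.3.3 as an explicit exception with a maximum dose and duration agreed with Merck. The documents give no figures for either. That route accepts some steroid exposure during pembrolizumab treatment, so the amended sentence in section 5.1.1.1 is the better choice.

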5.1.1 Dose Modifications and Dosing Delays

The following dose modification rules will be used with respect to potential toxicity. Toxicity will be assessed continuously according to the NCI Common Terminology Criteria for Adverse Events [Version 4.0 \(CTCAE v4.0\)](#)

The following dose modifications should be made for febrile neutropenia, and blood counts obtained on day one of each cycle. If more than one of these conditions applies, use the most stringent (i.e., the greatest dose reduction). **The AE may be due to pembrolizumab or**

vorinostat alone in which case the respective agent should be reduced. If overlapping toxicity is suspected both drugs may be reduced with the potential to re-escalate the non-offending agent. Given the very different nature of pembrolizumab and vorinostat/tamoxifen toxicities, separate tables are shown for individual agents.

No dose modification will be pursued for tamoxifen.

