5.1.1.1 Dose Modifications and Dosing Delays Tables for Drug Related Adverse Events

Hematologic toxicity

Neutropenia:

Neutropenia	Vorinostat	Tamoxifen
Febrile neutropenia		
ANC \geq 1000	100%	100%
ANC: 500-1000	Hold for until \leq grade 2 #, Restart at 75%: 300 mg qd for all subsequent cycles Second occurrence resume at 200 mg qd for all subsequent cycles Third occurrence: remove from study	100%
ANC: 0-500	Hold for until \leq grade 2 or less# Restart at 75%: 300 mg qd for all subsequent cycles Second occurrence resume at 200 mg qd for all subsequent cycles Third occurrence: remove from study	100%

#Patient with a dose delay for more than 3 weeks in the first 2 cycles will need to be replaced for toxicity and efficacy assessments.

Patients who developed a second episode of **febrile neutropenia** despite a dose modification will be removed from study.

Anemia

Hemoglobin	Vorinostat	Tamoxifen
>8 mg/dl	100 %: 400 mg qd	100%

6.5-8 mg/dl	75 %: 300 mg qd	100%
<6.5 mg/dl	50 %: 200 mg qd	100%

An alternative to dose modification would be the use of PRBC transfusion. This is not allowed in cycle one, but may be used at the discretion of the treating physician for subsequent cycles.

Thrombocytopenia

Platelets	Vorinostat	Tamoxifen
>75'000	100 %: 400 mg qd	100%
≤75'000	100 %: 400 mg qd	100%
≤50'000/mm ³	Hold until ≤grade 2 or less Restart at 75%: 300 mg qd for all subsequent cycles Second occurrence resume at 200 mg qd for all subsequent cycles Third occurrence: remove from study_	100%
≤25'000/mm ³	Hold until ≤grade 2 or less Restart at 75%: 300 mg qd for all subsequent cycles Second occurrence resume at 200 mg qd for all subsequent cycles Third occurrence: remove from study	100%

Non-hematological toxicities

Laboratory abnormalities must be clinically relevant and dose and drug related to prompt dose modifications.

Bilirubin	Vorinostat	Tamoxifen
≤1.5 mg/dl	100 %: 400 mg qd	100%
1.6 – 3.0 mg/dl	75 %: 300 mg qd	100%

>3.0 mg/dl	First occurrence: hold until \leq grade 2, 75 %: 300 mg qd Second occurrence: Hold until grade 2 or less, 50 %: 200 mg qd	100%
AST/ALT	Vorinostat	Tamoxifen
\leq 2.5 x ULN	100 %: 400 mg qd	100%
2.5-5 x ULN	First occurrence: 75 %: 300 mg qd Second occurrence: 50 %: 200 mg qd	100%

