diarrhea is accompanied by fever. If diarrhea is suspected to be linked to pembrolizumab and is \geq grade 3, hold dose until toxicity resolves to \leq grade 1, then resume at dose given in prior cycle.

Other Non-hematological Toxicities:

Laboratory abnormalities must be clinically relevant and dose and drug related to prompt dose modifications.

Give the following dose based on the worst toxicity encountered during the previous cycle:

Fatigue	Vorinostat	Tamoxifen
Grade 1	100%	100%
Grade 2	Hold until toxicity is \leq grade 1, then resume at dose given in prior cycle.	100%
Grade 3, 4	Hold until toxicity is \leq grade 1, then resume at 75% (or less) of dose given in the prior cycle. If grade 3 toxicity recurs despite dose reduction, decrease to 50 % of initial dose.	100%.

Other	Vorinostat	Tamoxifen
Grade 1	100%	100%
Grade 2	Hold until toxicity is \leq grade 1, then resume at dose given in prior cycle.	100%
Grade 3	Hold until toxicity is \leq grade 1, then resume at 75% (or less) of dose given in the prior cycle. If grade 3 toxicity recurs despite dose reduction, decrease to 50 % of initial dose.	100%
Grade 4	Discontinue protocol therapy.	100%

Vorinostat may be reduced for grade II fatigue, asthenia, weight loss or other constitutional symptoms if deemed in the best interest of the patient.

Effects on the Eye: Ocular disturbances, including corneal changes, decrement in color vision perception, retinal vein thrombosis, and retinopathy has been reported in patients receiving tamoxifen. An increased incidence of cataracts and the need for cataract surgery have been reported in patients receiving tamoxifen. If grade 3 or 4 ocular toxicities occur, both drugs should be stopped. Any rechallenge should be discussed with the study chair.

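### For recurrent grade 3 toxicity, the vorinostat step in the Fatigue and Other tables is fixed at 200 mg, so a patient already at 200 mg or below gets no decrease

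*Combined protocol and SAP*

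**What the plan says.** Section 5.1.1.1, under Other Non-hematological Toxicities, has a Fatigue table and an Other table. The grade 3 and 4 row for fatigue and the grade 3 row for other toxicities carry the same two steps for vorinostat:

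- **First event.** Hold to grade 1 or better, "then resume at 75% (or less) of dose given in the prior cycle".
- **Recurrence.** "If grade 3 toxicity recurs despite dose reduction, decrease to 50 % of initial dose".

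The first step is relative to the dose in the previous cycle. The second is relative to the starting dose, which Section 4.1.2 and Table 5.1 set at 400 mg per day, 5 days of 7, in all arms. Section 4.1.2 also says that capsules are 100 mg and are to be taken whole.

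Other rules in the same section can lower vorinostat before any grade 3 non-hematological event. For neutropenia and thrombocytopenia the first step is "Restart at 75%: 300 mg qd for all subsequent cycles" and the next is "Second occurrence resume at 200 mg qd for all subsequent cycles". The anemia, bilirubin and AST/ALT tables also have a 200 mg level. A note below the Fatigue and Other tables adds an optional route: "Vorinostat may be reduced for grade II fatigue, asthenia, weight loss or other constitutional symptoms".

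**The concern.** A dose-reduction rule should lower the dose whenever it is triggered. This one is anchored to the starting dose, so it does so only for patients above 200 mg. Neither row says what to do when grade 3 toxicity returns at 200 mg or below.

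Safety and tolerability is the second primary objective, and Section 4.1.2 lists fatigue among vorinostat's dose-limiting toxicities. The check after 6 patients per arm, under Interim Analyses in Section 8, reduces only pembrolizumab and refers vorinostat back to these guidelines, patient by patient. The tables are thus the plan's stated control on vorinostat dose. At stake is that a patient may resume a dose that has just produced recurrent grade 3 toxicity, and that sites may improvise differently.

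**Working it through.** **Inputs.** Starting dose 400 mg; capsule 100 mg, taken whole; 5 dosing days per week; 3-week cycles (Section 4.1.2, Table 5.1). First step: at most 75% of the prior-cycle dose. Recurrence step: 50% of the initial dose (Section 5.1.1.1).

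**The plan's own figures.** 0.75 × 400 = 300 mg and 0.50 × 400 = 200 mg. These match the 75% and 50% levels printed in the anemia, bilirubin and AST/ALT tables. The Fatigue and Other tables do not print 200 mg, but it follows from their wording.

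**Recurrence step at each current dose.**

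| Current dose | Recurrence step (0.50 × 400) | Change |
|---|---|---|
| 300 mg | 200 mg | 200 − 300 = −100 mg |
| 200 mg | 200 mg | 200 − 200 = 0 |
| 100 mg | 200 mg | 200 − 100 = +100 mg |

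**How a patient comes to be at 200 mg.**

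- Through the row itself: 400 mg, 300 mg after the first event, 200 mg after the first recurrence. A second recurrence then meets the same sentence.
- Through an earlier reduction to 300 mg, for cytopenia or under the optional grade II rule. A first grade 3 event then allows at most 0.75 × 300 = 225 mg, which is 200 mg in whole capsules.
- Through the first step's permission to go below 75%, for example directly from 400 to 200 mg.

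**How a patient comes to be at 100 mg.** After a second cytopenia the dose is 200 mg. A first grade 3 event then allows at most 0.75 × 200 = 150 mg, which is 100 mg in whole capsules. A recurrence after that meets a step of 200 mg.

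**Exposure at stake at 200 mg.** Staying at 200 mg is 200 × 5 = 1000 mg per week, or 3000 mg per cycle. One capsule level lower is 100 × 5 = 500 mg per week, or 1500 mg per cycle.

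**Does another rule supply the dose?** Section 5.1.1 has a tie-break: "If more than one of these conditions applies, use the most stringent (i.e., the greatest dose reduction". It follows text on febrile neutropenia and blood counts and chooses among conditions present together. It does not say what dose follows a recurrence of one toxicity. Sections 3.4 and 6.2.3 (unacceptable events, investigator judgment) and the 3-week limit on delays in Section 6.2 allow or prompt stopping but give no dose. Diarrhea at grade 3 or 4 (Section 4.1.2) and eye toxicity ("If grade 3 or 4 ocular toxicities occur, both drugs should be stopped") have their own stopping rules and fall outside the gap, as does the grade 4 row of the Other table.

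**The case against.** The best defence is that this is an ordinary two-step ladder that works as designed from 400 mg. The gap needs a third event, or a grade 3 event on top of an earlier reduction or a deeper first cut. The 100 mg case needs two cytopenias, a grade 3 event and its recurrence. No clinician would raise the dose then. Vorinostat is meant to be adjusted individually, grade 3 to 5 events are reviewed monthly by the Site Committee, and the investigator can always stop treatment. Much of this stands: it limits both frequency and harm. It does not supply the missing step, because the tables are what the plan points to for vorinostat dosing.

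Two stronger readings are tempting and are not supported.

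- A reader might infer that the row endorses two conflicting doses. The lead-in, "Give the following dose based on the worst toxicity encountered during the previous cycle", could be taken to allow the 75% clause to be applied again, giving 100 mg where the recurrence sentence gives 200 mg. But the row is sequential: the 75% clause covers the first event and the recurrence sentence covers later ones. That sentence also calls for a decrease, so resuming 200 mg in a patient on 200 mg does not clearly comply with it. What is missing is a workable next step.
- A reader might infer that the two tables omit a removal step that is standard in this protocol. The neutropenia, thrombocytopenia and AST/ALT above 5 × ULN rows do remove the patient at a third occurrence. The anemia, bilirubin and AST/ALT 2.5 to 5 × ULN rows do not. There is no uniform standard to breach.

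**Conclusion.** The point holds in a narrow form. The recurrence step gives a real decrease at 300 mg, none at 200 mg, and at 100 mg it literally names a dose twice the current one. The last is best read as an artefact of anchoring to the starting dose, not as an intended instruction to escalate. The 200 mg case carries the weight, because the row's own ladder leads there.

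This rests on two assumptions: that the initial dose means the 400 mg start, which the sister tables support, and that doses are given in whole 100 mg capsules, as Section 4.1.2 states. The number of patients affected cannot be derived from the documents and is probably small. Response rate, alpha and power are unaffected. Because a stated safety rule can return a dose that does not fall, and the repair is nearly free, it is worth amending.

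**What to change.** Replace only the recurrence sentence, in both rows. Suggested text:

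> If the same toxicity returns at grade 3 (grade 3 or 4 for fatigue) after a dose reduction, hold vorinostat to grade 1 or less, then restart at least one 100 mg level below the current dose and no higher than 200 mg. If no lower whole-capsule dose is available, discontinue vorinostat.

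At a recurrence this gives 200 mg or less from 300 mg, 100 mg from 200 mg, and discontinuation from 100 mg. The 400, 300, 200 mg path and the first-event rule stay as they are. Naming the same toxicity keeps a first grade 3 event in a patient already reduced for cytopenia under the first-event rule. Naming grade 4 for fatigue keeps the worse recurrence from being handled more leniently. The separate stopping rules for diarrhea and eye toxicity are unchanged.

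Whether to stop at 200 mg instead of allowing one step to 100 mg is a clinical choice for the sponsor's medical lead and is not part of the required change.

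Cost: one sentence in two rows, through an amendment under Section 9.4, with no extra visits, patients or procedures. The downside is that some patients with recurrent grade 3 toxicity at 200 mg or below will receive less vorinostat or stop it earlier.
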